**Table 14.2.1.46**  
Change from Baseline in BCVA by ETDRS of Study Eye by Visit (LOCF) via Wilcoxon Rank Sum Test  
(Full Analysis Set)

|  | K-321 QID
(N=XXX) | K-321 BID
(N=XXX) | Placebo
(N=XXX) |
|--|----------------------|----------------------|--------------------|
| Change from Baseline in BCVA
by ETDRS at Week 1 [1] |                      |                      |                    |
| n  | XX                   | XX                   | XX                 |
| Mean (SD)  | XX.X (XX.XX)         | XX.X (XX.XX)         | XX.X (XX.XX)       |
| Median   | XX.X                 | XX.X                 | XX.X               |
| Q1, Q3   | XX.X, XX.X           | XX.X, XX.X           | XX.X, XX.X         |
| Min, Max   | XX, XX               | XX, XX               | XX, XX             |
| Difference to Placebo [2]                              |                      |                      |                    |
| p-value by Wilcoxon Rank
Sum Test                   | X.XXXX               | X.XXXX               |                    |
| Hodges-Lehmann Estimate                                | X.X                  | X.X                  |                    |
| Moses 95% Confidence
Interval                       | (XX.X, XX.X)         | (XX.X, XX.X)         |                    |

....

Note: BCVA = Best Corrected Visual Acuity. ETDRS = Early Treatment Diabetic Retinopathy Study  
Baseline is defined as the last [redacted] measurement including unscheduled assessments prior to the  
[redacted] tration of first dose [redacted] plasty are  
[redacted] e given  
assessment. For the change from baseline, only patients with a value at both baseline visit and the  
specific post-baseline visit are included.  
[2] P-value is based on the Wilcoxon rank sum test. The median differences between the treatment groups and  
the Moses CIs were estimated with the Hodge-Lehmann method.  
Source Data: Listing 16.2.6.7

<DIRECTORY PATH>PROGRAM NAME Executed: DDMMYYYY hh:mm

Prog Notes: Repeat for scheduled visits.

**Table 14.2.1.47**  
Summary of BCVA by ETDRS by Central ECD Gradeability by Visit  
(Full Analysis Set)

Gradable Central Corneal ECD Images

|                          | K-321 QID
(N=XXX) | K-321 BID
(N=XXX) | Placebo
(N=XXX) | Total
(N=XXX) |
|--------------------------|----------------------|----------------------|--------------------|------------------|
| All Post-baseline |                      |                      |                    |                  |
| N                        | XX                   | XX                   | XX                 | XX               |
| Mean (SD)                | XX.X (XX.XX)         | XX.X (XX.XX)         | XX.X (XX.XX)       | XX.X (XX.XX)     |
| Median                   | XX.X                 | XX.X                 | XX.X               | XX.X             |
| Q1, Q3                   | XX.X, XX.X           | XX.X, XX.X           | XX.X, XX.X         | XX.X, XX.X       |
| Min, Max                 | XX, XX               | XX, XX               | XX, XX             | XX, XX           |
| Baseline          |                      |                      |                    |                  |
| N                        | XX                   | XX                   | XX                 | XX               |
| Mean (SD)                | XX.X (XX.XX)         | XX.X (XX.XX)         | XX.X (XX.XX)       | XX.X (XX.XX)     |
| Median                   | XX.X                 | XX.X                 | XX.X               | XX.X             |
| Q1, Q3                   | XX.X, XX.X           | XX.X, XX.X           | XX.X, XX.X         | XX.X, XX.X       |
| Min, Max                 | XX, XX               | XX, XX               | XX, XX             | XX, XX           |
| Week x            |                      |                      |                    |                  |
| N                        | XX                   | XX                   | XX                 | XX               |
| Mean (SD)                | XX.X (XX.XX)         | XX.X (XX.XX)         | XX.X (XX.XX)       | XX.X (XX.XX)     |
| Median                   | XX.X                 | XX.X                 | XX.X               | XX.X             |
| Q1, Q3                   | XX.X, XX.X           | XX.X, XX.X           | XX.X, XX.X         | XX.X, XX.X       |
| Min, Max                 | XX, XX               | XX, XX               | XX, XX             | XX, XX           |

....

Note: BCVA = Best Corrected Visual Acuity, ETDRS= Early Treatment Diabetic Retinopathy Study  
 ECD = Endothelial Cell Density  
 Baseline is defined as the last [redacted] measurement including unscheduled assessments prior to the  
 tion of first dose of [redacted]  
 [redacted] Central corneal ECD include [redacted] Central corneal ECD assessments or the Central corneal  
 o oedema.

Assessments after rescue keratoplasty are [REDACTED]

<DIRECTORY PATH>PROGRAM NA [REDACTED] ed: DDMMYYYY hh:mm  
Prog Notes: Continue with [REDACTED] Central Corneal ECD Images'.

**Table 14.2.1.48**  
Summary of BCVA by ETDRS by Central ECD Value by Visit  
(Full Analysis Set)

1 < Central ECD Value <= Mean

|                   | K-321 QID
(N=XXX) | K-321 BID
(N=XXX) | Placebo
(N=XXX) | Total
(N=XXX) |
|-------------------|----------------------|----------------------|--------------------|------------------|
| All Post-baseline |                      |                      |                    |                  |
| N                 | XX                   | XX                   | XX                 | XX               |
| Mean (SD)         | XX.X (XX.XX)         | XX.X (XX.XX)         | XX.X (XX.XX)       | XX.X (XX.XX)     |
| Median            | XX.X                 | XX.X                 | XX.X               | XX.X             |
| Q1, Q3            | XX.X, XX.X           | XX.X, XX.X           | XX.X, XX.X         | XX.X, XX.X       |
| Min, Max          | XX, XX               | XX, XX               | XX, XX             | XX, XX           |
| Baseline          |                      |                      |                    |                  |
| N                 | XX                   | XX                   | XX                 | XX               |
| Mean (SD)         | XX.X (XX.XX)         | XX.X (XX.XX)         | XX.X (XX.XX)       | XX.X (XX.XX)     |
| Median            | XX.X                 | XX.X                 | XX.X               | XX.X             |
| Q1, Q3            | XX.X, XX.X           | XX.X, XX.X           | XX.X, XX.X         | XX.X, XX.X       |
| Min, Max          | XX, XX               | XX, XX               | XX, XX             | XX, XX           |
| Week x            |                      |                      |                    |                  |
| N                 | XX                   | XX                   | XX                 | XX               |
| Mean (SD)         | XX.X (XX.XX)         | XX.X (XX.XX)         | XX.X (XX.XX)       | XX.X (XX.XX)     |
| Median            | XX.X                 | XX.X                 | XX.X               | XX.X             |
| Q1, Q3            | XX.X, XX.X           | XX.X, XX.X           | XX.X, XX.X         | XX.X, XX.X       |
| Min, Max          | XX, XX               | XX, XX               | XX, XX             | XX, XX           |

....

Note: BCVA = Best Corrected Visual Acuity, ETDRS= Early Treatment Diabetic Retinopathy Study  
 ECD = Endothelial Cell Density  
 Baseline is defined as the last [redacted] measurement including unscheduled assessments prior to the  
 administration of first dose of [redacted]  
 Assessments after rescue keratoplasty are [redacted]

<DIRECTORY PATH>PROGRAM NAME Executed: DDMMYYYY hh:mm

Prog Notes: Continue with 'Central ECD Value > Mean' and [REDACTED].

**Table 14.2.1.49**  
Correlation between BCVA by ETDRS and Central Corneal ECD (Include [REDACTED]) (Pearson and Spearman)  
(Full Analysis Set)

|                        | K-321 QID
(N=XXX) | K-321 BID
(N=XXX) | Placebo
(N=XXX) | Total
(N=XXX) |
|------------------------|----------------------|----------------------|--------------------|------------------|
| Pearson's Correlation  | 0.XX                 | 0.XX                 | 0.XX               | 0.XX             |
| Spearman's Correlation | 0.XX                 | 0.XX                 | 0.XX               | 0.XX             |

Note: BCVA = Best Corrected Visual Acuity, ETDRS= Early Treatment Diabetic Retinopathy Study  
 ECD = Endothelial Cell Density  
 Central corneal ECD assessments that are unable to be performed due [REDACTED].  
 Ass [REDACTED] be a [REDACTED] ed an [REDACTED] s [REDACTED].  
 or [REDACTED] by [REDACTED] [REDACTED] [REDACTED].  
 Ass [REDACTED] are [REDACTED].

<DIRECTORY PATH>PROGRAM NAME Executed: DDMMYYYY hh:mm

Table 14.2.1.50

Correlation between BCVA by ETDRS and Central Corneal ECD (Include [REDACTED] Data) (No Corneal Oedema)  
(Pearson and Spearman)  
(Full Analysis Set)

Same format as Table 14.2.1.49

Note: BCVA = Best Corrected Visual Acuity, ETDRS= Early Treatment Diabetic Retinopathy Study  
ECD = Endothelial Cell Density

Assessments before and after rescue keratoplasty are [REDACTED] as [REDACTED]  
or [REDACTED] by [REDACTED] are [REDACTED].  
Only [REDACTED] a observation [REDACTED].  
Assessments after rescue keratoplasty are [REDACTED].

<DIRECTORY PATH>PROGRAM NAME Executed: DDMMYYYY hh:mm

Table 14.2.1.51

Correlation between BCVA by ETDRS and Central Corneal ECD (Exclude [REDACTED] Data) (Pearson and Spearman)  
(Full Analysis Set)

Same format as Table 14.2.1.49

Note: BCVA = Best Corrected Visual Acuity, ETDRS= Early Treatment Diabetic Retinopathy Study  
ECD = Endothelial Cell Density

Central corneal ECD assessments that are unable to [REDACTED] and a [REDACTED] s  
[REDACTED] be analysed and categorized as [REDACTED] or [REDACTED]  
[REDACTED] are not included.  
[REDACTED] rescue keratoplasty are [REDACTED].

<DIRECTORY PATH>PROGRAM NAME Executed: DDMMYYYY hh:mm

Table 14.2.1.52

Correlation between BCVA by ETDRS and Central Corneal ECD (Exclude [REDACTED] Data) (No Corneal Oedema)  
(Pearson and Spearman)  
(Full Analysis Set)

Same format as Table 14.2.1.49

Note: BCVA = Best Corrected Visual Acuity, ETDRS= Early Treatment Diabetic Retinopathy Study

ECD = Endothelial Cell Density

Ass [REDACTED] be analysed and categorized as [REDACTED]

[figure not shown]
or [REDACTED] are not included.

Only [REDACTED] a observed are included.

Assessments after rescue keratoplasty are included using the collected values.

<DIRECTORY PATH>PROGRAM NAME Executed: DDMMYYYY hh:mm

Figure 14.2.1.42  
Time to Achieve Intervention of Rescue Therapy (Kaplan-Meier Plot)  
(Full Analysis Set)

Note: Time to Achieve Intervention of Rescue Therapy = Date of Achieving Intervention of Rescue Therapy - Day 1 + 1.

Patient is considered having received rescue therapy if the patient 1) received rescue surgical procedure (penetrating keratoplasty or endothelial keratoplasty) during the study. 2) withdrawal with potential for surgical procedure. 3) withdrawal with potential for Rho kinase Inhibitor treatment.]

Patient's study discontinuation date is used as the rescue therapy date if the patient withdrawal with potential for surgical procedure or Rho kinase Inhibitor treatment.

Patients who complete follow-up or discontinue the study without achieving the specified endpoint are

Source Data: T14.2.1.42

DIRECTORY PATH>PROGRAM NAME Executed: DDMMYYYY hh:mm

[figure not shown]
Programming note: Please show x-axis as Day 1 to Day 371. Please display y-axis label as 'Probability of Achieving Intervention of Rescue Keratoplasty (%)'.

Please display all treatment groups: K-321 QID, K-321 BID, Placebo

Figure 14.2.1.43

Central Corneal ECD (cells/mm^2) of Study Eye performed by Specular Microscopy (LOCF) (Time Series Plot) (Full Analysis Set)

Note: LOCF = last-observation-carried forward, ECD = Endothelial Cell Density  
Baseline is defined as the last measurement including unscheduled assessments prior to the administration of first dose of treatment.  
Central corneal ECD (both baseline and post-baseline) that are unable to be performed due to

assessment and analysis and central corneal ECD by [redacted] are [redacted].

[redacted]

T14 43

DIRECTORY PATH>PROGRAM NAME Executed: DDMMYYYY hh:mm

Programming note: Please show x-axis according to the analysis visit. Please display y-axis label as 'Mean(+/-SD) Central Corneal ECD (cells/mm^2) by Specular Microscopy'.  
Please display all treatment groups: K-321 QID, K-321 BID, Placebo  
Below the figure please include the N counts at each visit.  
Please include N counts for each treatment arm at the annotation.

Figure 14.2.1.44

Change from Baseline in Central Corneal Thickness ( $\mu\text{m}$ ) of Study Eye (LOCF) (Time Series Plot)  
(Full Analysis Set)

Repeat Figure 14.2.1.43 for Change from Baseline in Central Corneal Thickness

Note: Baseline is defined as the last [REDACTED] measurement including unscheduled assessments prior to  
inistration of first dose of st [REDACTED] n  
[REDACTED] central corneal [REDACTED]  
[REDACTED] atoplasty are [REDACTED]

[REDACTED] m baseline is defined as the post baseline value minus the baseline value for the given  
assessment. For the change from baseline, only patients with a value at both baseline visit and the  
specific post-baseline visit are included.

Source Data: T14.2.1.44

[figure not shown]
DIRECTORY PATH>PROGRAM NAME Executed: DDMMYYYY hh:mm

Programming note: Please show x-axis according to the analysis visit. Please display y-axis label as  
'Mean(+/-SD) Change from Baseline in Central Corneal Thickness ( $\mu\text{m}$ )'.

Please display all treatment groups: K-321 QID, K-321 BID, Placebo

Figure 14.2.1.45

Proportion of Patients Who Achieve No Corneal Oedema of Study Eye (LOCF) (Bar Chart)  
(Full Analysis Set)

Note: No corneal oedema is defined as absent of oedema in all three layers of cornea, including epithelial, stromal, and endothelial.

corneal oedema assessments are [REDACTED]. Patients who received a rescue keratoplasty are [REDACTED].

Numbers presented on the bars are the number of patients who achieve no corneal oedema of study eye for each visit under each treatment arm.

Source Data: T14.2.1.45

DIRECTORY PATH>PROGRAM NAME Executed: DDMMYYYY hh:mm

Programming note: Please show x-axis according to the analysis visit. Please display y-axis label as 'Proportion of Patients Who Achieve No Corneal Oedema'.

Please display all treatment groups on the same page: K-321 QID, K-321 BID, Placebo

Please include the n counts above each bar for each treatment arm and each visit for subjects who achieved the endpoint.

Figure 14.2.1.46  
Change from Baseline in BCVA by ETDRS of Study Eye (LOCF) via Wilcoxon Rank Sum Test (Time Series Plot)  
(Full Analysis Set)

[figure not shown]
Repeat Figure 14.2.1.43 for Change from Baseline in BCVA

Note: BCVA = Best Corrected Visual Acuity; ETDRS = Early Treatment Diabetic Retinopathy Study  
Baseline is defined as the last measurement including unscheduled assessments prior to the  
administration of first dose. [redacted]  
[redacted] surgery are  
[redacted] ven  
assessment. For the change from baseline, only patients with a value at both baseline visit and the  
specific post-baseline visit are included.  
Source Data: T14.2.1.46

DIRECTORY PATH>PROGRAM NAME Executed: DDMMYYYY hh:mm

Programming note: Please show x-axis according to the analysis visit. Please display y-axis label as  
'Mean(+/-SD) Change from Baseline in BCVA by ETDRS Letter Score'.  
Please display all treatment groups: K-321 QID, K-321 BID, Placebo

Figure 14.2.1.47  
BCVA by ETDRS by Central ECD Gradeability by Visit (Box Plot)  
(Full Analysis Set)

Note: BCVA = Best Corrected Visual Acuity, ETDRS= Early Treatment Diabetic Retinopathy Study  
ECD = Endothelial Cell Density  
Baseline is defined as the last [REDACTED] measurement including unscheduled assessments prior to the  
[REDACTED] tion of first dose of [REDACTED]  
[REDACTED] Central corneal ECD include [REDACTED] Central corneal ECD assessments or the Central corneal  
[REDACTED] ments that could not be performed [REDACTED] o oedema.  
Source Data: Table 14.2.1.47

[figure not shown]
DIRECTORY PATH>PROGRAM NAME Executed: DDMMYYYY hh:mm

Programming note: Please show x-axis according to the subgroups [REDACTED] and [REDACTED]. Please  
display y-axis label as 'BCVA by ETDRS Letter Score'.

Please display 'All Post-Baseline Visits' in the first page, then start the second page with  
'Baseline', 'Week X'... Each visit should be on a separate page.

In each page please display all treatment groups and Total: Total, K-321 QID, K-321 BID, Placebo  
In each page please include number of subjects under each treatment arm and subgroups under the plot.

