IEC	independent ethics committee
IOP	intra-ocular pressure
IRB	institutional review board
IWRS	interactive web response system

Abbreviation	Definition
LOCF	last-observation-carried-forward
M/N	morning and night
MD/E	mid-day and evening
MedDRA	Medical Dictionary for Regulatory Activities
MHRA	Medicines and Healthcare Products Regulatory Agency
NCS	not clinically significant
PPS	per-protocol set
QID	4 times daily
ROCK	Rho-associated protein kinase
SAE	serious adverse event
SAP	statistical analysis plan
SFS	safety set
SOA	schedule of study site activities
SUSAR	suspected unexpected serious adverse reaction
TEAE	treatment-emergent adverse event
UK	United Kingdom
US	United States

List of Terms

Term	Definition
Descemetorhexis	Removal of an area of roughened and irregular Descemet membrane along with central guttae (also referred to herein as Descemet membrane stripping)

1 Introduction

In the early 20th century, Ernst Fuchs described a bilateral corneal dystrophy now referred to as Fuchs endothelial corneal dystrophy (FECD). The primary defect in FECD seems to be related to the endothelial cells that normally sit on a modified basement membrane (Descemet's membrane) that lines the inner surface of the cornea.

In the normal adult human cornea, the endothelial cell density (ECD) on Descemet's membrane is in the range of 2,000 to 3,500 cells/mm² ([Ianchulev et al 2019](#)) and the endothelial cells maintain the cornea in a state of relative dehydration, which preserves corneal transparency. During adulthood there is continuous loss of endothelial cells at an approximate rate of 0.6% per year. Since the number of endothelial cells cannot increase because of a state of mitotic arrest, gaps caused by apoptosis are filled by the migration of adjacent cells that increase in size and change shape. The function of the corneal endothelium can be maintained while the ECD is maintained above approximately 400 cells/mm². Below that threshold (due to disease, trauma or old age), there is decompensation of the endothelial pumping mechanism and corneal oedema produces a visual haze ([Van den Bogerd et al 2018](#)).

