5.8.2 Rescue Surgical Procedures

Penetrating keratoplasty or endothelial keratoplasty may be offered as rescue surgical procedures to an enrolled patient if the investigator judges that endothelial healing is not complete at Week 12 (Visit 9), or earlier if the investigator considers that the patient needs urgent treatment. If the rescue surgery is performed, the dosing with study drug must be

discontinued immediately (without tapering) and the patient will attend all planned study visits including the follow-up period.

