The correlation between BCVA (letters) by ETDRS and Central Corneal ECD will be assessed by using Pearson's and Spearman's correlation coefficients. The correlation scatter plot will also be presented. The correlations and scatter plots will be based on data from all visits combined and analysed for all subjects overall as well as by each treatment arm. The correlations will be assessed separately using different data scenario:

- In the first correlation analysis, the data handling methods will be the same as primary analysis for [REDACTED] Central corneal ECD assessments, or the Central corneal ECD assessments that could not be performed due to oedema. Otherwise, the analysis will be [REDACTED]. Patients who receive a rescue keratoplasty will also be [REDACTED].
- The second correlation analysis will be the same as first except that the analysis visits where corneal oedema is observed or the Central corneal ECD assessments that could not be performed due to oedema will be [REDACTED].
- In the third analysis, the analysis visits where there are [REDACTED] Central corneal ECD assessments, or the Central corneal ECD assessments that could not be performed due to oedema will be [REDACTED]. Otherwise, the analysis will include the same data as the first correlation analysis.
- The fourth correlation analysis will be the same as third except that the analysis visits where corneal oedema is observed or the Central corneal ECD assessments that could not be performed due to oedema will be [REDACTED].

The BCVA (letters) by ETDRS will be summarized by the Central corneal ECD subgroups (defined below as sub-groupings (A) and (B)) at each visit and across all post-baseline visits by each treatment arm and all treatment arms combined. Box plots will also be presented for each at each visit and across all post-baseline visits by each treatment arm and all treatment arms combined for sub-grouping definition (A). Scatter plot and correlation coefficient (Spearman) will also be presented for each subgroup at each visit and across all post-baseline visits by each treatment arm and all treatment arms combined for sub-grouping definition (B). [REDACTED] Central corneal ECD include [REDACTED] Central corneal ECD assessments or the Central corneal ECD assessments that could not be performed due to oedema. Central corneal ECD assessments

that are [REDACTED] due to other reasons are [REDACTED]. Patients who receive a rescue keratoplasty will also be [REDACTED].

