**Figure 14.2.1.51**  
Correlation between BCVA by ETDRS and Central Corneal ECD (Exclude [REDACTED] Data) (Pearson and Spearman)  
(Full Analysis Set)

Repeat Figure 14.2.1.49 but only include the visits where there is no imputed data.

Note: BCVA = Best Corrected Visual Acuity, ETDRS= Early Treatment Diabetic Retinopathy Study  
ECD = Endothelial Cell Density  
Central corneal ECD assessments that are unable to [REDACTED] and a [REDACTED] es  
[REDACTED] be analysed and categorized as [REDACTED] or [REDACTED]  
[REDACTED] are not included.  
[REDACTED] rescue keratoplasty are [REDACTED].  
Source Data: Table 14.2.1.51

<DIRECTORY PATH>PROGRAM NAME Executed: DDMMYYYY hh:mm

Programming note: Please display x-axis label as 'Central Corneal ECD (cells/mm^2)'. Please display y-axis label as 'BCVA by ETDRS Letter Score'.  
Please display the scatter lot for total and each treatment group in separate pages.  
Please include the spearman and perason correlation values and the corresponding p-values under the figure for each treatment group and total.

Figure 14.2.1.52

Correlation between BCVA by ETDRS and Central Corneal ECD (Exclude [REDACTED] Data) (No Corneal Oedema)  
(Pearson and Spearman)  
(Full Analysis Set)

Repeat Figure 14.2.1.49 but only include the visits where there is no imputed data and the visits where there is No Corneal Oedema.

Note: BCVA = Best Corrected Visual Acuity, ETDRS= Early Treatment Diabetic Retinopathy Study

ECD = Endothelial Cell Density

Ass [REDACTED] be analysed and categorized as [REDACTED]

or [REDACTED] are not included.

Only [REDACTED] a obs

Assessments after rescue keratoplasty are [REDACTED]

Source Data: Table 14.2.1.52

<DIRECTORY PATH>PROGRAM NAME Executed: DDMMYYYY hh:mm

Programming note: Please display x-axis label as 'Central Corneal ECD (cells/mm^2)'. Please display y-axis label as 'BCVA by ETDRS Letter Score'.

Please display the scatter lot for total and each treatment group in separate pages.

Please include the spearman and perason correlation values and the corresponding p-values under the figure for each treatment group and total.

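### Table 14.2.1.52 pools visits after rescue keratoplasty with native-endothelium visits, which can dilute or inflate the BCVA–ECD correlation (mainly Pearson's r) if graft cell density is well above native

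*SAP*

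**What the plan says.** The note to Table 14.2.1.52 (SAP addendum, Appendix 1) reads: "Assessments after rescue keratoplasty are included using the collected values". That table reports the fourth data scenario of SAP addendum Section 2. On pooling, Section 2 says: "based on data from all visits combined and analysed for all subjects overall as well as by each treatment arm". The association is "assessed by using Pearson's and Spearman's correlation coefficients".

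The matching figure shell, Figure 14.2.1.52, is to "only include the visits where there is no imputed data and the visits where there is No Corneal Oedema". Neither filter refers to rescue surgery.

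Protocol Section 5.8.2 defines rescue as penetrating or endothelial keratoplasty and says that afterwards "the patient will attend all planned study visits including the follow-up period". Protocol Table 6-1 schedules both specular microscopy and BCVA at Weeks 16, 20, 24, 38 and 52, so post-graft pairs are due to be collected.

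The sentence on rescue is blacked out in Section 2, in the notes to Tables 14.2.1.49 to 14.2.1.51 and in the note to Figure 14.2.1.52. It is legible only for Table 14.2.1.52.

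**The concern.** Protocol Section 1 describes endothelial keratoplasty as replacing the stripped area with donor endothelium. After rescue, central ECD therefore counts donor cells, and BCVA is that of a grafted eye. Before rescue, the same two measurements describe native cells that have repopulated the stripped area. The study's primary objective concerns the second situation.

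The filters in Table 14.2.1.52 also select unevenly. In an eye that fails to heal, oedematous native visits are dropped, while clear visits after the graft are kept. A failed eye can then contribute mostly graft data.

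A reader of this table will probably take the coefficient as evidence on whether higher ECD after descemetorhexis goes with better vision. If graft counts lie well above native counts, a small number of grafted rows can carry much of Pearson's r. The effect is larger in an arm with more rescues, so coefficients could differ between arms because of rescue frequency alone.

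**Working it through.** The documents give no correlation value to reproduce, so the check has two parts.

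**1. Do post-graft rows reach the coefficient?** The legible note includes them, Protocol 5.8.2 keeps the patients attending, Section 2 pools all visits, and a clear graft with a readable image passes both filters. So they do, by the stated rule.

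**2. How far could they move it?**

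From the documents:
- Normal adult ECD "is in the range of 2,000 to 3,500" cells/mm² (Protocol Section 1). This is only a proxy for donor tissue.
- The 700 cells/mm² responder threshold (Protocol 7.2). This is only a proxy for healed native ECD.
- About 60 patients, 1:1:1.
- In the literature summarised in Protocol Section 1, 31 of 47 corneas cleared (16 did not), and rescue grafts were done at 4 to 8.5 months. That is 17.3 to 36.8 weeks (months × 52/12), leaving four (Weeks 20, 24, 38, 52) down to two (Weeks 38, 52) scheduled visits.

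Assumed, not in the documents:
- 350 native rows.
- 6 rescued eyes × 4 visits = 24 graft rows.
- BCVA SD 8 letters, and no correlation within graft rows.
- Mean BCVA of grafted eyes minus native eyes, d, from −5 to +8 letters.
- Setting A: native 700 (SD 200), graft 2,200 (SD 250). Setting B: native 900 (SD 350), graft 1,500 (SD 350).

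Let p be the graft share of rows, D the difference in mean ECD, r the native correlation, s_x and s_y the native SDs, and g_x the graft ECD SD. For the pooled rows:
- cov = (1−p)·r·s_x·s_y + p(1−p)·D·d
- var(ECD) = (1−p)·s_x² + p·g_x² + p(1−p)·D²
- var(BCVA) = s_y² + p(1−p)·d²

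Here p = 24/374 = 0.0642 and p(1−p) = 0.0601.

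*Setting A, r = 0.40.* SD(ECD) = √(37,433 + 4,011 + 135,120) = 420.2.
- d = 0: 598.9 / (420.2 × 8) = **0.18**
- d = −5: (598.9 − 450.4) / (420.2 × 8.093) = **0.04**
- d = +8: (598.9 + 720.6) / (420.2 × 8.237) = **0.38**

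With r = 0: −450.4 / 3,400.6 = **−0.13** to 720.6 / 3,461.1 = **+0.21**.

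*Setting B, r = 0.40.* SD(ECD) = √(122,500 + 21,619) = 379.6.
- d = 0: 1,048.1 / (379.6 × 8) = **0.35**
- d = −5: 868.0 / (379.6 × 8.093) = **0.28**
- d = +8: 1,336.4 / (379.6 × 8.237) = **0.43**

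With r = 0: **−0.06** to **+0.09**.

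Simulated means agree with these to within 0.01.

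*Leverage.* A row at the graft mean has leverage relative to the average of [1 + (graft mean − pooled mean)²/var(ECD)]/2. This is 6.1 in A and 1.6 in B. If graft ECD is near native ECD, it stays close to 1.

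*Fewer rows.* With 12 graft rows in A, 0.40 becomes 0.23 at equal vision and 0.14 at 5 letters worse.

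*One arm (117 native rows), setting A.* Two rescued eyes (8 rows) give 0.18 at equal vision. Four (16 rows) give 0.13, or −0.05 at 5 letters worse.

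*Sign change.* The covariance turns negative only if p·D·|d| exceeds r·s_x·s_y with d negative. With 24 rows and r = 0.40, A needs 640/96.3 = 6.6 letters worse and B needs 1,120/38.5 = 29 letters worse.

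*Spearman (simulation, A, 24 rows).* A native value of 0.38 becomes 0.27 to about 0.42. With 48 graft rows and grafted eyes 5 letters worse it is still 0.19, where Pearson is −0.05.

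**The case against.** The strongest reply is that the size of the effect rests entirely on undocumented inputs. Graft ECD, native post-operative ECD and the number of rescues are not given, and the quoted normal range is for healthy adult corneas, not grafts. This stands: setting B is as compatible with the documents as setting A, and there the distortion is modest.

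It is also fair to say that Spearman is reported beside Pearson and limits the effect, and that scatter plots accompany the coefficients, so a separate graft cluster might be visible. Four clear, gradable visits per rescued eye is at the high end. The addendum's rescue definition also counts withdrawals with potential for surgery or Rho kinase inhibitor treatment, and those withdrawals add no post-graft rows. Section 2 does not restrict the correlation to native healing, so that purpose is inferred. These points reduce the stakes. They do not make a single coefficient across two kinds of endothelium easier to interpret.

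Some stronger readings are tempting but not supported:
- *Graft rows are high-leverage outliers.* They are only if graft ECD is well above native.
- *The correlation will be reversed.* That needs a large ECD contrast together with clearly worse vision in clear grafted eyes or many rescues. Mean Spearman did not reverse in any scenario examined.
- *All four correlation tables are affected.* Section 2 builds the later scenarios on the first by cross-reference, which hints at a common rule, but the rule is blacked out everywhere except Table 14.2.1.52.
- *The rule contradicts the handling of rescue in the primary analysis.* That text is blacked out too, so no comparison is possible.

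**Conclusion.** The point holds for Table 14.2.1.52. Its stated rule mixes donor and native endothelium in one pooled coefficient, and no legible filter separates them. If graft ECD is well above native ECD, Pearson's r can be diluted even when grafted and native eyes see equally well (0.40 to 0.18 in setting A, to 0.35 in setting B), or shifted away from zero when there is no native association (up to +0.21 or down to −0.13 in A; +0.09 or −0.06 in B). Arms with more rescues are affected more, and Spearman less. All figures are illustrations on assumed inputs, not estimates for this trial.

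SAP addendum Section 1 says these analyses were defined after the Week 12 unmasking, and Section 2 presents them as additional. The primary and secondary tests are not touched. This is an inexpensive improvement to an exploratory table, not a threat to the trial's main conclusion.

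**What to change.** In Table 14.2.1.52, report Pearson and Spearman with study-eye assessments on or after the date of rescue keratoplasty excluded. Keep the version with all collected values as a supplement. State the number of rows and eyes excluded in each arm. In Figure 14.2.1.52, show post-graft points with a separate symbol and say which points the printed coefficients and p-values cover.

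Apply the same change to Tables and Figures 14.2.1.49 to 14.2.1.51 only if their blacked-out rule is the same.

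The cost is a changed note, a date filter and one extra run. The main coefficient loses some rows, all of them from grafted eyes, and nothing collected is discarded because the supplement retains it.
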